9. CCI [REDACTED]

- [REDACTED]
- [REDACTED]
- [REDACTED]
- [REDACTED]
- [REDACTED]

10. CCI [REDACTED]

- [REDACTED]
- [REDACTED]
- [REDACTED]
- [REDACTED]
- [REDACTED]

11. CCI [REDACTED]

- [REDACTED]
- [REDACTED]
- [REDACTED]
- [REDACTED]
- [REDACTED]

12. CCI [REDACTED]

- [REDACTED]
- [REDACTED]
- [REDACTED]
- [REDACTED]
- [REDACTED]

13. CCI [REDACTED]

- [REDACTED]
- [REDACTED]
- [REDACTED]
- [REDACTED]
- [REDACTED]

14. CCI [REDACTED]

- [REDACTED]
- [REDACTED]
- [REDACTED]
- [REDACTED]
- [REDACTED]
- [REDACTED]

Appendix 9. Patient-Oriented Eczema Measure (POEM)

Please circle one response for each of the seven questions below about your eczema.
Please leave blank any questions you feel unable to answer.

1. Over the last week, on how many days has your skin been itchy because of your eczema?

No days 1–2 days 3–4 days 5–6 days Every day

2. Over the last week, on how many nights has your sleep been disturbed because of your eczema?

No days 1–2 days 3–4 days 5–6 days Every day

3. Over the last week, on how many days has your skin been bleeding because of your eczema?

No days 1–2 days 3–4 days 5–6 days Every day

4. Over the last week, on how many days has your skin been weeping or oozing clear fluid because of your eczema?

No days 1–2 days 3–4 days 5–6 days Every day

5. Over the last week, on how many days has your skin been cracked because of your eczema?

No days 1–2 days 3–4 days 5–6 days Every day

6. Over the last week, on how many days has your skin been flaking off because of your eczema?

No days 1–2 days 3–4 days 5–6 days Every day

7. Over the last week, on how many days has your skin felt dry or rough because of your eczema?

No days 1–2 days 3–4 days 5–6 days Every day

Total POEM Score (Maximum 28): _____

Appendix 10. Dermatology Life Quality Index (DLQI)

The aim of this questionnaire is to measure how much your skin problem has affected your life OVER THE LAST WEEK. Please tick (X) one box for each question.

- | | | | | |
|---|------------------------------------|-----------------------------------|-------------------------------------|---|
| 1. Over the last week, how itchy, sore, painful or stinging has your skin been? | Very much  | A lot  | A little  | Not at all  |
| 2. Over the last week, how embarrassed or self conscious have you been because of your skin? | Very much  | A lot  | A little  | Not at all  Not relevant  |
| 3. Over the last week, how much has your skin interfered with you going shopping or looking after your home or garden ? | Very much  | A lot  | A little  | Not at all  Not relevant  |
| 4. Over the last week, how much has your skin influenced the clothes you wear? | Very much  | A lot  | A little  | Not at all  Not relevant  |
| 5. Over the last week, how much has your skin affected any social or leisure activities? | Very much  | A lot  | A little  | Not at all  Not relevant  |
| 6. Over the last week, how much has your skin made it difficult for you to do any sport ? | Very much  | A lot  | A little  | Not at all  Not relevant  |
| 7. Over the last week, has your skin prevented you from working or studying ? | Yes  | No  | | |
| If "No", over the last week how much has your skin been a problem at work or studying ? | A lot  | A little  | Not at all  | |
| 8. Over the last week, how much has your skin created problems with your partner or any of your close friends or relatives ? | Very much  | A lot  | A little  | Not at all  Not relevant  |
| 9. Over the last week, how much has your skin caused any sexual difficulties ? | Very much  | A lot  | A little  | Not at all  Not relevant  |
| 10. Over the last week, how much of a problem has the treatment for your skin been, for example by making your home messy, or by taking up time? | Very much  | A lot  | A little  | Not at all  Not relevant  |

Please check you have answered EVERY question. Thank you.

DERMATOLOGY LIFE QUALITY INDEX (DLQI) – INSTRUCTIONS FOR USE

The Dermatology Life Quality Index questionnaire is designed for use in adults, i.e. patients over the age of 16. It is self-explanatory and can be simply handed to the patient who is asked to fill it in without the need for detailed explanation. It is usually completed in one or two minutes.

SCORING

The scoring of each question is as follows:

Very much	Scored 3
A lot	Scored 2
A little	Scored 1
Not at all	Scored 0
Not relevant	Scored 0
Question 7, 'prevented work or studying'	Scored 3

The DLQI is calculated by summing the score of each question resulting in a maximum of 30 and a minimum of 0. The higher the score, the more quality of life is impaired.

HOW TO INTERPRET MEANING OF DLQI SCORES

0–1	No effect at all on patient's life
2–5	Small effect on patient's life
6–10	Moderate effect on patient's life
11–20	Very large effect on patient's life
21–30	Extremely large effect on patient's life

REFERENCES

Finlay AY and Khan GK. Dermatology Life Quality Index (DLQI): a simple practical measure for routine clinical use. *Clin Exp Dermatol* 1994; **19**:210-216.

Appendix 11. **CCI** [Redacted]

[Redacted]

CCI	[Redacted]	[Redacted]
[Redacted]	[Redacted]	[Redacted]
[Redacted]	[Redacted]	[Redacted]
[Redacted]	[Redacted]	[Redacted]
[Redacted]	[Redacted]	[Redacted]
[Redacted]	[Redacted]	[Redacted]
[Redacted]	[Redacted]	[Redacted]
[Redacted]	[Redacted]	[Redacted]
[Redacted]	[Redacted]	[Redacted]
[Redacted]	[Redacted]	[Redacted]
[Redacted]	[Redacted]	[Redacted]
[Redacted]	[Redacted]	[Redacted]
[Redacted]	[Redacted]	[Redacted]
[Redacted]	[Redacted]	[Redacted]
[Redacted]	[Redacted]	[Redacted]
[Redacted]	[Redacted]	[Redacted]
[Redacted]	[Redacted]	[Redacted]
[Redacted]	[Redacted]	[Redacted]
[Redacted]	[Redacted]	[Redacted]
[Redacted]	[Redacted]	[Redacted]

[Redacted]

Appendix 12. Global Assessment of Change–AD

The following question will be asked at Week 16:

Overall, compared to the start of the study, how would you rate your atopic dermatitis symptoms over the past week?

- 1 = Much better
- 2 = Moderately better
- 3 = A little better
- 4 = No difference
- 5 = A little worse
- 6 = Moderately worse
- 7 = Much worse

7. DETERMINATION OF SAMPLE SIZE29

8. CHANGES IN THE PLANNED ANALYSES.....29

9. REFERENCES.....29

Change History:

Version	Date	Summary of Changes	Author
1.0	14AUG2018	Original document	PPD
		
Made administrative changes and corrected typos as needed.
 
Updated Section 6.1 to add MedDRA and WHO dictionary versions.
 
Added new Section Visit Windowing for ADIQ as 6.1.4.
 
Updated Section 6.1.6 to note only missing data up to the Week 16 visit will be imputed.
 
Updated Section 6.1.7.1 to add imputation method for sensitivity analysis adjusting for subjects that use a rescue medication.
 
Updated Section 6.1.7.2 to add imputation method for sensitivity analysis adjusting for subjects that use a rescue medication.
 
Updated Section 6.11 Prior and Concomitant Medications to include how to handle missing dates.
 
Updated Section 6.12 Rescue Medications to define how rescue medications will be identified.
 
Updated Section 6.13.1 to remove the overall test.
 
Updated Section 6.13.2 to remove the overall tests.
 
Updated 6.13.3 to account for observed and rescue medication sensitivity analyses.
 
Updated Section 6.13.3.2 to remove part on rescue medications.
 
Added Section 6.13.3.3 to add sensitivity analyses adjusting for subjects that use rescue medications.
	
2.0	25FEB2019	Updated Section 6.14 Other Supportive Efficacy Analyses to add by time point analyses Days 2	PPD

		
through 7 for Sleep-Loss and Pruritus Numerical Rating Scales.
 
Updated Section 6.14 Other Supportive Efficacy Analyses to remove the following endpoint: Frequency and percent distributions of the dichotomized Sleep-loss NRS will be summarized at Weeks 2, 4, 6, 8, 10, 12, 14, and 16 and time points Days 2 through 7.
 
Updated Section 6.15.1 Extent of Exposure to clarify the definitions of missed injections and expected number of injections.
 
Updated Section 6.15.2 Anti-Drug Antibody (ADA) Data to include NAb analysis.
 
Updated Section 6.15.4 Adverse Events for defining treatment-emergent AEs when the start date of the AE is missing.
	
--	--	--	--

1. LIST OF ABBREVIATIONS AND DEFINITIONS OF TERMS

AD	atopic dermatitis
ADA	anti-drug antibody
ADIQ	Atopic Dermatitis Impact Questionnaire
AE(s)	adverse event(s)
ANCOVA	analysis of covariance
ATC	anatomical therapeutic chemical
BSA	body surface area
CMH	Cochran-Mantel-Haenszel
DLQI	Dermatology Life Quality Index
EASI	Eczema Area and Severity Index
ECG	Electrocardiogram
g/dL	grams per deciliter
HADS	Hospital Anxiety and Depression Scale
HR	heart rate
IGA	Investigator Global Assessment
IL	interleukin
IWRS	interactive web response system
LOCF	last observation carried forward
LSMean	least square mean
max	maximum
MCMC	Markov Chain Monte Carlo
MedDRA	Medical Dictionary for Regulatory Activities
mITT	modified intent-to-treat
mg	milligram
min	minimum
n	number of observations
N	number of subjects (sample size)
NRI	non-response imputation
NRS	numerical rating scale
PK	pharmacokinetic
POEM	Patient Oriented Eczema Measure
PP	per-protocol
PT	preferred term
Q2W	every 2 weeks

Q4W	every 4 weeks
QST	QST Consultations, Ltd.
QTcB	Q-T interval corrected for heart rate using Bazett's formula
QTcF	Q-T interval corrected for heart rate using Fridericia's formula
SAE(s)	serious adverse event(s)
SAS®	Statistical Analysis System (SAS® Institute Inc., Cary, NC)
SD	standard deviation
SOC	system organ class
TEAE(s)	treatment-emergent adverse event(s)
WHO-DDE	World Health Organization Drug Dictionary Enhanced

2. INTRODUCTION

Atopic dermatitis (AD) is a relapsing and remitting inflammatory skin disorder that affects all age groups [1]. It is chronic, incurable, and is characterized by skin-barrier disruption and immune dysregulation (largely mediated by type-2 helper T cells) [1]. Clinically, AD is characterized by xerosis, erythematous crusted eruption (dermatosis), lichenification, an impaired skin barrier, and intense pruritus [2]. AD flares are frequently triggered by exposure to environmental factors, irritants, and allergens [3].

Lebrikizumab is a humanized monoclonal immunoglobulin G4 antibody with a mutation in the hinge region for increased stability. Lebrikizumab binds specifically to soluble human interleukin (IL)-13 with high affinity, and potently inhibits IL-13 signaling through the IL-4R α /IL-13R α 1 complex. Because lebrikizumab binds to IL-13 in a non-receptor binding domain (i.e., a portion of the molecule not involved in binding to its receptor), antibody-bound IL-13 can still bind its receptor (IL-13 R α 1), but the receptor complex is not activated.

Study DRM06-AD01 is designed to evaluate multiple dose levels of lebrikizumab and to demonstrate the dose response of lebrikizumab in the treatment of moderate-to-severe AD. The effect of lebrikizumab will be assessed as a monotherapy (without concomitant topical corticosteroids). The dose levels tested—125 mg every 4 weeks (Q4W), 250 mg Q4W, and 250 mg every 2 weeks (Q2W)—were chosen to determine the optimal dose for treatment of moderate-to-severe AD. Loading doses of lebrikizumab will be used in the active-treatment groups to allow drug to reach steady state quickly (after the first dose in the Q4W dose groups, and after the second dose in the Q2W dose group).

3. STUDY OBJECTIVES

To evaluate the safety and efficacy of lebrikizumab compared with placebo in patients with moderate-to-severe AD.

To evaluate the dose-response of lebrikizumab in patients with moderate-to-severe AD.

4. STUDY DESIGN

4.1 Overall Study Design

This is a randomized, double-blind, placebo-controlled, parallel-group study. Approximately 275 patients with moderate-to-severe AD will be enrolled into this 32-week study.

Patients will be seen every 2 weeks and receive all study drug injections in the clinic. Patients will be evaluated for safety and efficacy through Week 16 on study. A safety follow-up visit will occur at Week 24 and a follow-up phone call will occur at Week 32.

Serum PK and anti-drug antibody (ADA) will be collected from all patients. PK samples will be collected at Baseline, Weeks 2, 4, 8, 12, 16, and 24. ADA samples will be collected at Baseline, Weeks 2, 4, 16, and 24.

Patients will be randomized 3:3:3:2 to one of 4 treatment groups, each described below.

Treatment Group 1: Lebrikizumab, 125 mg Q4W

Baseline: Loading dose of 250 mg (2 injections of 1 mL of 125 mg/mL drug product and 2 injections of 1-mL placebo)

Week 2: Four 1-mL injections of placebo

Weeks 4, 8, 12: 125 mg (one 1-mL injection of 125 mg/mL drug product and one 1-mL injection of placebo)

Weeks 6, 10, 14: Two 1-mL injections of placebo

Treatment Group 2: Lebrikizumab, 250 mg Q4W

Baseline: Loading dose of 500 mg (four 1-mL injections of 125 mg/mL drug product)

Week 2: Four 1-mL injections of placebo

Weeks 4, 8, 12: 250 mg (two 1-mL injections of 125 mg/mL drug product)

Weeks 6, 10, 14: Two 1-mL injections of placebo

Treatment Group 3: Lebrikizumab, 250 mg Q2W

Baseline and Week 2: Loading dose of 500 mg (four 1-mL injections of 125 mg/mL drug product)

Week 4, 6, 8, 10, 12, 14: 250 mg (two 1-mL injections of 125 mg/mL drug product)

Treatment Group 4: Placebo Q2W

Baseline and Week 2: Four 1-mL injections of placebo

Week 4, 6, 8, 10, 12, 14: Two 1-mL injections of placebo

4.1.1 Schedule of Visits and Assessments

The schedule of assessments can be found in Appendix 1 (Schedule of Visits and Procedures) of the protocol.

4.1.2 Method of Assigning Subjects to Treatment Groups

A randomization schedule will be generated by a member of the QST Consultations, Ltd. (QST) Statistical Services department who is not associated with the conduct or analysis of the study, using a validated system. The randomization list will not be stratified.

At the Baseline/Day 1 visit, qualified subjects will be randomized to treatment using an IWRS. The interactive web response system (IWRS) will assign a study drug kit number based on a predetermined randomization schedule. The kit number will be recorded in the electronic case report form. Approximately 225 subjects will be randomized to active treatment and approximately 50 subjects will be randomized to placebo treatment for a total of approximately 275 subjects. Subjects will be randomized to treatment groups in such a manner to balance treatment allocation in a 3:3:3:2 fashion (lebrikizumab, 125 mg Q4W: lebrikizumab, 250 mg Q4W: lebrikizumab, 250 mg Q2W: placebo Q2W).

4.1.3 Blinding

The Sponsor or designee, the Investigator, study-site personnel, and the patient will be blinded to treatment assignment. The integrity of the clinical study will be maintained by observing the treatment blind. If knowledge of a patient's treatment assignment is required for the patient's clinical care and/or safety, the Investigator will open the Code Breaking Card received with the study-drug kit. The Code-Breaking Card should be stored in a secure, locked location at the site. The Investigator should have access to the Code-Breaking Card at all times (e.g., 24/7). The Investigator should consult with the Sponsor's medical monitor prior to obtaining treatment assignment information. The Investigator must document (in the patient's medical record) the date and time the blind was broken, the names of the personnel involved, and the reason that treatment assignment information was required.

5. EFFICACY AND SAFETY ENDPOINTS

5.1 Efficacy Endpoints

For all efficacy evaluations the measurement endpoint is defined at Week 16.

5.1.1 Primary Efficacy Endpoint

The primary efficacy endpoint is:

- The percent change in Eczema Area and Severity Index (EASI) from Baseline to Week 16.

5.1.2 Secondary Efficacy Endpoints

The secondary efficacy endpoints are as follows:

- Proportion of patients with a 75% improvement from Baseline in EASI (EASI75) at Week 16.
- Proportion of patients with an Investigator Global Assessment (IGA) score of 0 (clear) or 1 (almost clear) and a reduction ≥ 2 points from Baseline to Week 16.
- Proportion of patients with EASI < 7 at Week 16.
- Proportion of patients achieving EASI50 and EASI90 at Week 16.
- Percent change in sleep-loss numerical rating scale (NRS) score from Baseline to Week 16.
- Percent change in pruritus NRS score from Baseline to Week 16.
- Proportion of patients with pruritus NRS change of ≥ 3 point improvement from Baseline to Week 16.
- Proportion of patients with pruritus NRS change of ≥ 4 point improvement from Baseline to Week 16.
- Absolute and percent change in Body Surface Area (BSA) involved with AD from Baseline to Week 16.
- Absolute and percent change in Atopic Dermatitis Impact Questionnaire (ADIQ) score from Baseline to Week 16.

5.2 Safety Endpoints

Safety will be assessed through adverse events (AEs), serum chemistry, hematology, urinalysis, and serology laboratory testing, electrocardiogram (ECG) testing, physical examination, vital signs, and pharmacokinetics (PK). The planned PK analysis will be included in a separate PK Analysis Plan.

6. STATISTICAL AND ANALYTICAL PLANS

6.1 General Methodology

All statistical processing will be performed using SAS® unless otherwise stated. No interim analyses are planned.

Except where noted, all statistical tests will be two-sided and will be performed at the 0.05 level of significance. The inclusion of p-values in the efficacy analyses is to assist in characterizing the therapeutic efficacy of the active medication. No adjustments will be made for multiple comparisons for the efficacy analyses. The primary analysis will be performed when all patients have completed the treatment phase at Week 16. The final time-course data analysis will be performed when all patients have finished Week 32.

Descriptive statistics will be used to provide an overview of the efficacy and safety results. For categorical parameters, the number and percentage of patients in each category will be presented. The denominator for percentage will be based on the number of patients appropriate for the analysis. For continuous parameters, descriptive statistics will include the number of patients (n), mean, standard deviation (SD), median, and range. Appropriate inferential statistics will be used for the primary and secondary efficacy variables.

The primary method of handling missing efficacy data will be the method of Markov Chain Monte Carlo (MCMC) multiple imputation.

The primary analysis will be performed when all patients have completed the treatment phase at Week 16.

Reported AEs, medical history terms and prior and concomitant procedures and therapies will be classified on the basis of Medical Dictionary for Regulatory Activities (MedDRA) terminology version 20.1. Prior and concomitant medications will be classified on the basis of World Health Organization Drug Dictionary Enhanced (WHO-DDE) terminology version March 2017.

6.1.1 Statistical Analysis

All analyses will be performed by QST using SAS® Version 9.3 or later. All summary tables and data listings will be prepared utilizing SAS® software.

The standard operating procedures of QST will be followed in the creation and quality control of all data displays and analyses.

6.1.2 Baseline Definition

Baseline is defined as the last non-missing assessment prior to first dose of study drug.

6.1.3 Visit Windowing

Efficacy data will be summarized based on nominal visit indications with the exception of data captured at early termination and unscheduled visits. Efficacy data from early termination and unscheduled visits will be summarized based on mapped visit values. The analysis windows for early termination and unscheduled visits are presented in the following table.

Analysis Windows for Efficacy Assessments

Scheduled Visit	Target Study Day	Window (Days)
Week 2	15	9 to 22
Week 4	29	23 to 36
Week 6	43	37 to 50
Week 8	57	51 to 64
Week 10	71	65 to 78
Week 12	85	79 to 92
Week 14	99	93 to 106
Week 16	113	107 to 127
Week 20	141	128 to 158
Week 24	169	159 to 197
Week 32	225	198 to 239

Efficacy data collected prior to study day 9 for early termination and unscheduled visits will not be analyzed, with the exception of those identified as baseline values. Efficacy data collected at early termination and unscheduled visits after study day 239 will not be included in analyses.

The definition for the study day included in each study window is defined below:

Study Day prior to Day 1 = Visit Date – Day 1 Date

Study Day on or after Day 1 = Visit Date – Day 1 Date + 1

If an assessment's mapped visit is a visit at which the subject has data from a scheduled visit present, or if no analyses are planned for the assessment at the mapped visit, the data collected at the early termination or unscheduled visit will not be included in analyses.

In the event of multiple values from unscheduled or early termination assessments within an analysis window, the value closest to the scheduled visit target study day will be used for analyses. If two values tie as closest to the time point (for example, one value is before and the other value is after the time point), then the later value will be selected.

Safety data will be summarized based on nominal visit indications. Data captured at early termination will be assigned an Analysis Window visit based on the "Analysis Windows for Efficacy Assessments" above. Unscheduled visits will not be summarized.

Data collected at all visits will be included in the data listings with visit presented as reported by the site, except for subject reported electronic diary data. Subject reported electronic diary data listings will be presented with analysis visit, since there is no site reported visit.

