7.2 Baseline Visit (Day 1)

- Confirm emollient use.
- Re-assess and confirm patient eligibility (Inclusion/Exclusion criteria).
- Measure weight and vital signs.
- Collect concomitant medication and procedure/therapy information.
- Query for adverse events (AEs) since the last visit.
- Collect a 12-lead ECG.
- Draw blood samples for laboratory tests (hematology and chemistry)
- Draw a pre-dose blood sample for PK and anti-drug antibody (ADA) testing.
- Conduct urine for urinalysis and urine pregnancy test (WOCBP only).
- Dispense electronic tablet that will be used for home recording of pruritus NRS and sleep-loss NRS (daily), and ADIQ (weekly).
- Train patient on the use of the electronic tablet.
- Review compliance report on the electronic tablet for the assessments (pruritus NRS, sleep-loss NRS, and ADIQ) and remind patient to record daily.
- Complete the following assessments:
 - Investigator’s Global Assessment (IGA)
 - Eczema Area and Severity Index (EASI)
 - Body Surface Area (BSA)
 - Patient Oriented Eczema Measure (POEM)
 - Dermatology Life Quality Index (DLQI)
 - Hospital Anxiety and Depression Scale (HADS).
- Randomize the patient.
- Administer study drug.
- Instruct the patient to apply an emollient twice daily.
- Schedule next visit.

7.3 Visits on Day 15, Day 29, Day 43, Day 57, Day 71, Day 85 and Day 99 (+/- 3 Day)

- Confirm emollient use.

- Measure vital signs.
- Collect concomitant-medication information.
- Review and record AEs.
- Review compliance report on the electronic tablet for the daily assessments (pruritus NRS, sleep-loss NRS, and ADIQ) and remind patient to continue daily record.
- At **Day 29, 57, and 85**, draw blood samples for laboratory tests, and collect urine for urinalysis and pregnancy test (WOCBP only).
- At **Day 29, 57, and 85**, complete the following assessments:
 - Investigator’s Global Assessment (IGA)
 - Eczema Area and Severity Index (EASI)
 - Body Surface Area (BSA)
- At **Day 57** complete the following assessments:
 - Dermatology Life-Quality Index (DLQI)
 - Hospital Anxiety and Depression Scale (HADS).
- At **Day 15, 29, 57, and 85**, collect blood samples for PK (see Section 8.2.2 for instructions).
- At **Day 15 and 29**, collect a pre-dose blood sample for ADA testing (see Section 8.2.2 for instructions).
- Administer study drug.
- Remind the patient to apply an emollient twice daily.
- Remind the patient to use the tablet daily.
- Schedule next visit.

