6.1.4 Visit Windowing for ADIQ

ADIQ is recorded by the subjects using an electronic diary with the date of entry recorded. Since ADIQ is not captured at the clinic for a specific visit the ADIQ diary data will be windowed into the appropriate study visit for analysis as outlined below.

Baseline ADIQ

The baseline ADIQ will be identified using the definition in Section 6.1.2 Baseline Definition.

Post-baseline ADIQ

First, an ADIQ recorded on the same day as a study visit will be mapped to that study visit and flagged for analysis if occurring at a scheduled study visit. If a visit ranges over multiple days the start date of the visit will be used for mapping. Note, unscheduled and early termination visits will be mapped to planned study visits using Section 6.1.3 Visit Windowing prior to this step. All remaining ADIQ will be mapped using the analysis windows presented in the following table.

Analysis Windows

Scheduled Visit	Target Study Day	Window (Days)
Week 2	15	9 to 22
Week 4	29	23 to 36
Week 6	43	37 to 50
Week 8	57	51 to 64
Week 10	71	65 to 78
Week 12	85	79 to 92
Week 14	99	93 to 106
Week 16	113	107 to 127
Week 20	141	128 to 158
Week 24	169	159 to 197
Week 32	225	198 to 239
Note: Only visits up through week 16 will be flagged for ADIQ analysis.		

If multiple ADIQ are mapped to the same analysis visit selecting an ADIQ to be flagged for analysis will follow the following steps.

- 1) If the subject had the corresponding visit, the ADIQ closest to the actual visit day will be flagged. If two ADIQ are equidistant to the actual visit day the ADIQ prior to the planned study day will be flagged.

If the subject missed the corresponding visit, the ADIQ closest to the actual planned study day will be flagged. If two ADIQ are equidistant to the planned study day the ADIQ prior to the planned study day will be flagged.

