6.1.6 Handling of Dropouts or Missing Data

Missing 16 week efficacy data will be imputed and subsequently analyzed. The primary method of handling missing efficacy data will be the method of MCMC multiple imputation which does not rely on the assumption of data missing at random. Additionally, the pattern of missing observations in each treatment group will not influence the missing value estimation in the other because the imputation will be conducted independently for each treatment group. The mITT population analyses and summaries on EASI and IGA will use the MCMC multiple imputation method to impute missing values up to the Week 16 visit. Missing data for Post-Week 16 visits will not be imputed.

The multiple imputation process for imputing missing EASI and IGA data and subsequent analysis will involve 4 distinct phases with these principal tasks:

1. Calculate the number of missing 16 week values for each treatment group to be estimated by MCMC. Let n_{miss} be the maximum number of missing among the two treatment groups.
2. Create a data set of subjects, one for each treatment group, with observed values and those needing estimation by MCMC. The missing values in each data set will be filled in using the MCMC method '5 x n_{miss} ' times to generate '5 x n_{miss} ' data sets. The resulting data sets for each treatment arm will be combined into one complete data set for each imputation.
3. For each complete data set, compute the necessary derived variables. Each complete data set will be analyzed with the appropriate analysis model. See Sections 6.1.5.1.1 and 6.1.5.1.2 for details.

Analyses using the Cochran-Mantel-Haenszel (CMH) statistics will be normalized using the Wilson-Hilferty transformation [4] prior to combining them using SAS® PROC MIANALYZE.

The results from these analyses will be combined into a single inference using SAS® PROC MIANALYZE.

Per-protocol population analyses and summaries on EASI and IGA will use the last observation carried forward (LOCF) imputation method to impute missing values up to the Week 16 visit. Missing data for Post-Week 16 visits will not be imputed.

Sensitivity analyses on some of the secondary efficacy variables will use non-response imputation (NRI) to impute missing values.

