6.13.3.2 Repeated Measures Analyses on Observed Data

The second set of sensitivity analyses will be performed on observed data. The primary endpoint of percent change from baseline in EASI score at Week 16 will be analyzed with a repeated measures ANCOVA, with treatment, visit (Weeks 4, 8, 12, and 16), and treatment by visit interaction as factors, and a covariate of baseline EASI score.

The two dichotomized secondary endpoints of IGA and EASI75 at Week 16 will each be analyzed with a repeated measures logistic regression model (generalized estimating equations), with the dichotomized endpoint as the dependent variable and treatment, visit (Weeks 4, 8, 12, and 16), and treatment by visit interaction as factors.

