6.14 Other Supportive Efficacy Analyses

Descriptive statistics will be presented for the following parameters by treatment group for both the mITT and PP populations:

- Descriptive statistics will be used to summarize EASI at each evaluation from Baseline through Week 24.
- Descriptive statistics will be used to summarize the absolute and percent change in EASI will be summarized at Weeks 4, 8, 12, 16, 20, and 24.
- Frequency and percent distributions of the dichotomized EASI score will be summarized at Weeks 4, 8, 12, 16, 20, and 24.
- Frequency and percent distributions of the IGA score will be summarized at each evaluation from Baseline through Week 24.
- Frequency and percent distributions of the dichotomized IGA scores will be summarized at Weeks 4, 8, 12, 16, 20, and 24.

- Descriptive statistics will be used to summarize Sleep-loss NRS will be summarized at each visit from Baseline through Week 16 and time points Days 2 through 7. Baseline (Day 1) – Day 7 are nominal study days from the date of first study drug injection (Day 1).
- Descriptive statistics will be used to summarize absolute and percent change in Sleep-loss NRS will be summarized at Weeks 2, 4, 6, 8, 10, 12, 14, and 16 and time points Days 2 through 7. Baseline (Day 1) – Day 7 are nominal study days from the date of first study drug injection (Day 1).
- Descriptive statistics will be used to summarize Pruritus NRS will be summarized at each visit from Baseline through Week 16 and time points Days 2 through 7. Baseline (Day 1) – Day 7 are nominal study days from the date of first study drug injection (Day 1).
- Descriptive statistics will be used to summarize absolute and percent change in Pruritus NRS will be summarized at Weeks 2, 4, 6, 8, 10, 12, 14, and 16 and time points Days 2 through 7. Baseline (Day 1) – Day 7 are nominal study days from the date of first study drug injection (Day 1).
- Frequency and percent distributions of the dichotomized Pruritus NRS will be summarized at Weeks 2, 4, 6, 8, 10, 12, 14, and 16 and time points Days 2 through 7. Baseline (Day 1) – Day 7 are nominal study days from the date of first study drug injection (Day 1).
- Descriptive statistics will be used to summarize BSA will be summarized at each evaluation from Baseline through Week 24.
- Descriptive statistics will be used to summarize absolute and percent change in BSA will be summarized at Weeks 4, 8, 12, 16, and 24.

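### Does dropping most early-termination EASI scores before Week 16 harm the imputation behind the primary endpoint?

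*SAP*

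**What the plan says.** The protocol schedules EASI during treatment at "Day 29, 57, and 85" (Protocol 7.3) and at Day 113, and requires it at the early-termination visit (Protocol 7.4).

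SAP 6.1.3 assigns early-termination and unscheduled efficacy data to windows that also exist for Weeks 2, 6, 10 and 14. It then says that "if no analyses are planned for the assessment at the mapped visit, the data collected at the early termination or unscheduled visit will not" be used. A score is also dropped if the mapped visit already holds scheduled data.

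The planned EASI analyses name their weeks. The repeated measures model in SAP 6.13.3.2 is fitted "with treatment, visit (Weeks 4, 8, 12, and 16), and treatment by visit interaction as factors, and a covariate of baseline EASI score". In SAP 6.14, "Frequency and percent distributions of the dichotomized EASI score will be summarized at Weeks 4, 8, 12, 16, 20, and 24", and change from baseline has the same list. One line there is looser: "Descriptive statistics will be used to summarize EASI at each evaluation from Baseline through Week 24".

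On imputation, SAP 6.1.6 says "The mITT population analyses and summaries on EASI and IGA will use the MCMC multiple imputation method to impute missing values" up to Week 16. The construction step is "Create a data set of subjects, one for each treatment group, with observed values and those needing estimation by MCMC". No visits or variables are listed. The text of SAP 6.13.1 is not in the copy available here, so nothing is claimed about it.

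**The concern.** The last score before a patient leaves is the observed value closest to the missing Week 16 value. Some dropout depends on severity: under Protocol 6.10 a patient who needs systemic therapy for AD is discontinued from the study. If the imputation cannot see the score that explains the departure, it fills Week 16 from earlier, better scores and overstates improvement in that arm. A patient who leaves at Week 6 would be imputed from baseline and Week 4 only. One whose early-termination visit falls on Days 9 to 22 would be imputed from baseline alone.

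The only sensitivity analysis of percent change in EASI in SAP 6.13.3 uses the same four visits, so it would not reveal the problem. Because SAP 6.1.6 lists no inputs, two programmers could also build different data sets for the primary endpoint. A natural response is to give EASI windows matched to its own schedule: Days 9-42 to Week 4, 43-70 to Week 8 and 71-106 to Week 12, keeping any scheduled score already present.

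**Working it through.** **1. Days affected (windows from SAP 6.1.3).**
- Days 9 to 106 hold 7 windows of 14 days: 7 x 14 = 98.
- Weeks 2, 6, 10 and 14, with no planned EASI analysis: 4 x 14 = 56; 56/98 = 57%.
- Days after target in the Week 4, 8 and 12 windows, if the scheduled visit took place on target: 3 x 7 = 21. Total 56 + 21 = 77; 77/98 = 79%.
- With the matched windows, the excluded days are 30-42 (13), 58-70 (13) and 86-106 (21): 47; 47/98 = 48%.
- Newly admitted days: 9-22 (14), 43-50 (8) and 71-78 (8), so 30 = 77 - 47. All of them precede the target day to which they are assigned, by up to 29 - 9 = 20 days.

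These are shares of calendar days. The documents give no dropout timing, so the share of actual scores is unknown.

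**2. Precision.** Group sizes of 75 and 50 come from Protocol 11.2; an SD of 30 for percent change is assumed. SE = 30 x sqrt(1/75 + 1/50) = 5.48.

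**3. Bias (simulation; every input is an assumption).** Day 113 mean change is -40% on placebo and -65% on active, Week 16 SD is 28-31, and dropout is 12-35% on placebo and 10-24% on active. Scores are imputed within arm from baseline and Weeks 4, 8, 12 and 16. There are 24 scenarios with dropout driven by severity or flare. A negative arm bias means that improvement is overstated; a positive difference bias means a shift toward no effect.

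| Bias, percentage points | 6.1.3 applied to the imputation | Matched windows |
|---|---|---|
| Placebo mean | -1.53 to -0.21 | -0.57 to +0.17 |
| Active mean | -1.00 to -0.13 | -0.34 to +0.27 |
| Difference | -0.02 to +0.68 | +0.01 to +0.51 |
| Difference, equal dropout | -0.10 to +0.26 | -0.01 to +0.45 |
| Per arm, dropout unrelated to severity | at most 0.10 | at most 0.42 |

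The largest difference bias is 0.68/5.48 = 0.12 SE. A repeat run gave up to 0.79, and 0.79/5.48 = 0.14 SE. In a further repeat the mean absolute difference bias was 0.22 points under 6.1.3 and 0.17 with the matched windows (0.04 and 0.03 SE). It was smaller with the windows in only 14 of 24 scenarios.

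**4. Where the arm-level gain comes from.** Mean absolute arm bias with the matched windows is 0.29 of its value under 6.1.3, a reduction of about 70%. Every newly used score is earlier than its label, however, and early scores show less improvement. That mistiming pushes against the bias. Once mapped scores are shifted for the mean time trend, the ratio is 0.55, a 45% reduction.

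**5. Rescue.** Suppose rescue has made every early-termination score 10 points better and the target is the value without rescue. The difference bias is then larger with the matched windows in 16 of 24 scenarios; at 20 points it is larger in all 24.

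**The case for a change.** The case for a change is a fair one. The reading of SAP 6.1.3 is correct, the day counts reproduce, and the data are collected anyway. The matched windows reduced arm-level bias in all 24 placebo and all 24 active scenarios (23 of 24 active in a repeat run), and arm-level means matter in a dose-ranging trial. The looser line in SAP 6.14 hardly rescues the text, because EASI is not scheduled at Weeks 2, 6, 10 or 14.

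What stands is the text, the direction of the arm-level bias, and the fact that SAP 6.1.6 does not name its inputs. The case for new windows does not stand:

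- They leave out the scores nearest Week 16. After an attended Week 12 visit, Days 86 to 106 are still dropped.
- They sit badly with SAP 6.1.6, which uses one imputation for both analyses and summaries. A Day 15 score would be the Week 4 value for the Week 16 imputation but missing at Week 4 in the by-visit summary.
- ADIQ is no precedent. It has its own section because "Since ADIQ is not captured at the clinic for a specific visit the ADIQ diary data will be windowed into the appropriate study visit", and its windows have the same limits as those in 6.1.3.
- No consistent gain appeared for EASI75 or IGA response.

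The missing list of inputs has limited reach. The NRI analyses do not use these scores. The rescue-adjusted analyses in SAP 6.1.7 count patients who stopped treatment early as non-responders. LOCF belongs mainly to the per-protocol set, which requires the Week 16 visit except for patients who left because of a related AE.

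**Conclusion.** No change to the plan is needed. Two things are involved.

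The first is a gap that analysts fill sensibly. SAP 6.1.6 does not list the imputation inputs, but SAP 6.1.3, 6.13.3.2 and the dated lists in 6.14 all point to baseline and Weeks 4, 8, 12 and 16 after windowing. Recording that in the programming specification before unblinding is ordinary practice.

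The second is a trade-off between small biases. Under assumed severity-driven dropout, leaving out these early-termination scores overstates mean EASI improvement by about 0.1 to 1.5 points per arm. It moves the treatment difference by at most about 0.8 points, less than 0.15 SE, toward no effect. Matched windows bring almost no gain in that difference and none when dropout is equal. They add bias when dropout is unrelated to severity, and can do harm if rescue has altered the scores.

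These sizes rest on assumed dropout, response and SD, since the documents give none of them. The day counts rest only on the SAP windows and, for 77 of 98, on visits attended on target. Heavier dropout, or a larger imbalance between arms than was assumed, could enlarge the bias.
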